SAE	Serious Adverse Event
SD	Stable disease
SRS	Stereotactic radiosurgery
T2/FLAIR	T2 Weighted fluid attenuated inversion recovery
TKI	Tyrosine kinase inhibitor
UAP	Unanticipated Problem
UCCC	University of Colorado Cancer Center
UCD	University of Colorado Denver
WBRT	Whole-brain radiotherapy

1 PROTOCOL SUMMARY

1.1 SYNOPSIS

Protocol Title:

Brigatinib Before Brain Irradiation Trial (B3i Trial): A Phase II Trial of Brigatinib Alone for Brain Metastases from ALK+ Lung Cancer

Objectives:

- ***Primary Objective:***
 1. To evaluate if CNS control is acceptable with a strategy of brigatinib alone for patients with ALK+ lung cancer with brain metastases
- ***Secondary Objectives:***
 1. To evaluate time until progression with brigatinib alone
 2. To evaluate overall survival with a strategy of brigatinib alone
 3. To evaluate the best CNS objective response rates (ORR) with brigatinib alone
 4. To evaluate the time until the administration of WBRT with brigatinib alone
 5. To evaluate longitudinal changes in quality of life with brigatinib alone

Endpoint:

- ***Primary Endpoint:***
 1. Disease Control Rate (DCR) of brain metastases at 3 months (13-week MRI ± 7 days) where DCR is defined as complete response (CR), partial response (PR), or stable disease (SD) as defined by the RANO-BM criteria.
- ***Secondary Endpoints:***
 - 1a. Time until any CNS progressive disease (PD) by RANO-BM criteria and rates at follow up intervals (up to 24 months from Day 1).
 - 1b. Time until any local PD (ie, in brain lesions identified at the time of enrollment) by RANO-BM criteria and rates at follow up intervals (up to 24 months from Day 1).
 - 1c. Time until any distant brain PD (ie, new brain lesions that were not present at the time of enrollment) by RANO-BM criteria and rates at follow up intervals (up to 24 months from Day 1).
 - 1d. Time until progression at any site using RANO-BM for intracranial disease and RECIST for extracranial disease and rates at follow up intervals (up to 24 months from Day 1).

- 2a. Time until death from any cause and rates at follow up intervals (up to 24 months from Day 1).
- 2b. Time until brain metastases-specific mortality, defined as intracranial progression as a component of cause of death and rates at follow up intervals (up to 24 months from Day 1).
3. Cumulative rate of best responses individually for complete response (CR), partial response (PR), stable disease (SD), by RANO-BM criteria
4. Time until the administration of whole brain-radiotherapy (WBRT) and rates at follow up intervals (up to 24 months from Day 1).
5. Quality of life will be assessed using standardized QOL metrics (EORTC QLQ C30/BN 20)

- ***Exploratory:***

1. Analysis of blood at baseline and at progression to correlate blood-based markers with clinical outcomes.
2. To characterize corticosteroids administration before and after brigatinib initiation

Population:

- **Sample size**

- Maximum number of participants that can be enrolled is 35 (allow for screen failures)
- Minimum number of participants to be enrolled 19 (number of participants needed to answer scientific question/aims)

- **Gender** Male and Female
- **Age Range** 18-100 years
- **Demographic group:** Patients with brain metastases from ALK+ lung cancer without prior treatment with brigatinib
- **General health status:** ECOG ≤2
- **Geographic location:** United States

Phase:

II

Participating Sites:

University of Colorado, Mayo Rochester, City of Hope Los Angeles

Description of Study Intervention:

Brigatinib, an oral tyrosine kinase inhibitor (TKI) targeting anaplastic lymphoma kinase (ALK)

[figure not shown]
Study Duration:

4 years

Participant Duration:

2 years

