5.4 SCREEN FAILURES

Patients who have signed informed consent and subsequently fail to meet the inclusion and/or exclusion criteria are defined as screen failures. Once the investigator determines that screening will not continue for a patient, and the patient will not be enrolled in the study, the screen failure should be documented. Patients who screen fail may later be re-screened with prior sponsor-investigator approval.

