9.2 SAMPLE SIZE DETERMINATION

The goal of this single arm phase 2 trial is to demonstrate specifically the short-term safety and efficacy of a strategy of brigatinib alone for patients with asymptomatic or mildly symptomatic brain metastases. Using contemporary prospective data on brigatinib (Camidge, et al. "Exploratory Analysis of Brigatinib Activity in Patients with Anaplastic Lymphoma Kinase-Positive Non-Small-Cell Lung Cancer and Brain Metastases in Two Clinical Trials" Journal of Clinical Oncology (2018): JCO-2017), our alternate hypothesis (H_1) is that brigatinib alone will result in a CNS disease control rate (DCR) of 90% at 3 months in this population. An upper 1-sided 1-sample exact binomial test with 19 analyzable patients will have 88.5% power to detect a difference between the null hypothesis (H_0) of 60% or less DCR and H_1 , assuming a type-1 error rate of 0.025. Assuming a 20% dropout rate, it is expected that 23 patients would need to be enrolled to yield 19 evaluable patients (i.e. completers).

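### The synopsis gives 19 as the minimum to be enrolled, but 19 is the evaluable number; at the plan's 20% dropout, about 24 must be enrolled to expect 19 evaluable

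*Combined protocol and SAP*

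**What the plan says.** The population part of the synopsis (section 1.1) gives two limits. The lower one reads "Minimum number of participants to be enrolled 19 (number of participants needed to answer scientific question/aims". The upper one reads "Maximum number of participants that can be enrolled is 35 (allow for screen failures".

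Section 9.2 attaches the same 19 to a different group: "An upper 1-sided 1-sample exact binomial test with 19 analyzable patients will have 88.5% power to detect a difference". It then adds the dropout allowance: "Assuming a 20% dropout rate, it is expected that 23 patients would need to be enrolled to yield 19 evaluable patients", and explains evaluable patients as completers. Section 9.4.6 repeats a design of about 23 enrolled for 19 evaluable, and allows an initial primary analysis once 19 evaluable patients have had the 3-month brain MRI. Section 9.3 restricts the primary analysis to enrolled patients who start brigatinib and have the 13-week MRI.

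Section 5.4 describes screen failures as people who consented and then failed the criteria. In saying when to document the failure, it refers to the point at which "the patient will not be enrolled in the study".

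**The concern.** Read literally, the synopsis says that 19 enrolled patients are enough to answer the study question. Under 9.3 every patient lost before the 13-week MRI leaves the primary analysis, so 19 enrolled gives 19 analysed only if nobody is lost. The plan itself expects to lose one in five.

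The synopsis minimum is the only numerical enrolment floor in the documents. Section 7.1 lists unsatisfactory enrolment as a reason to terminate but gives no threshold, and 9.4.6 plans no interim efficacy or futility analysis. A trial closed at 19 enrolled would satisfy the synopsis and most likely fall short of the power in 9.2. A negative result would still carry weight, since 2.3.3 says that unacceptable control rates would support the historic practice of adding CNS radiotherapy.

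The upper limit adds to the confusion. It is called an enrolment maximum but makes room for screen failures, whom 5.4 treats as not enrolled.

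**Working it through.** **Inputs, all from section 9.2.** Null rate p0 = 0.60 ("of 60% or less DCR"). Alternative p1 = 0.90 ("brigatinib alone will result in a CNS disease control rate (DCR) of 90% at 3 months in this population"). One-sided level 0.025 ("assuming a type-1 error rate of 0.025"). Dropout 20%. Evaluable n = 19.

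**Method.** For n evaluable patients, the cut-off r is the smallest integer with P(X ≥ r | n, 0.60) ≤ 0.025. Power is P(X ≥ r | n, 0.90).

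**Step 1: the plan's own figure.** For n = 19, r = 16. Exact size is 0.0230 and power is 0.8850. The stated 88.5% is reproduced.

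**Step 2: expected evaluable patients at 20% dropout.**
- 19 enrolled: 19 × 0.80 = 15.2
- 23 enrolled: 23 × 0.80 = 18.4
- 24 enrolled: 24 × 0.80 = 19.2
- Enrolment needed for 19 expected: 19/0.80 = 23.75, so 24

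The plan's 23 matches 19 × 1.2 = 22.8 rounded up, or a dropout of 1 − 19/23 = 17.4%.

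**Step 3: power at each evaluable number.**

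| Evaluable n | Cut-off r | Exact size | Power at 0.90 |
|---|---|---|---|
| 14 | 13 | 0.0081 | 58.5% |
| 15 | 14 | 0.0052 | 54.9% |
| 16 | 14 | 0.0183 | 78.9% |
| 17 | 15 | 0.0123 | 76.2% |
| 18 | 16 | 0.0082 | 73.4% |
| 19 | 16 | 0.0230 | 88.5% |

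For n = 15 by hand: power = 15 × 0.9^14 × 0.1 + 0.9^15 = 0.3432 + 0.2059 = 0.549. A cut-off of 13 of 15 just fails, with size 0.0271. That is why 15 is a low point and why power rises by 24 points at 16.

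**Step 4: average over random dropout.** Exact power is saw-toothed, so one value of n is a poor summary. Let the evaluable number M follow Bin(N, 0.80), with the cut-off recomputed for each M. Average power = Σ P(M = m) × power(m).

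| Enrolled N | Average power | P(at least 19 evaluable) |
|---|---|---|
| 19 | 66.4% | 0.80^19 = 1.4% |
| 23 | 79.8% | 50.1% |
| 24 | 82.0% | 65.6% |

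On this common basis, 19 rather than 23 enrolled costs 79.8 − 66.4 = 13.4 points.

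**The case against.** The strongest reply is that nobody is told to stop at 19. A floor is not a target. Sections 9.2 and 9.4.6 both plan for about 23 enrolled, 9.4.6 ties the initial analysis to 19 evaluable patients, and the ceiling of 35 leaves room to get there. The synopsis gloss on 19 may simply mean the analysable count under the wrong label. All of this stands, and it limits the point to an inconsistency in the synopsis, with a loss of power that depends on how the floor is used.

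Three stronger readings are tempting, and the documents support none of them.

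- *The trial has 55% power instead of 88.5%.* The 88.5% is stated only for 19 analysable patients and is right for them. The 54.9% belongs to exactly 15 evaluable, the lowest value anywhere from n = 13 to n = 24. Setting one against the other gives a gap of 33.6 points, but it compares a figure with dropout to a figure without. The like-for-like loss is 13.4 points.
- *The dropout inflation is materially wrong.* The gap between 23 and 24 is one patient, and 9.4.6 says approximately 23. It is worth tidying while the text is open, and no more.
- *Screen failures count within the 19, so the shortfall is larger still.* The synopsis attaches that allowance to the maximum only. Its parenthesis explains what 35 covers, and 5.4 mentions enrolment only in saying when to document a failure. The wording is loose, but it does not show that the minimum is counted that way.

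**Conclusion.** The point holds as a labelling error in a stated sample-size figure. The synopsis presents 19 enrolled as sufficient, while 9.2, 9.3 and 9.4.6 make 19 the evaluable number and need about 23 enrolled to obtain it. The hypothesis test, its cut-off of 16 of 19 and the 88.5% are sound.

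If accrual did end at the synopsis minimum, about 15 patients would be evaluable, and average power would be about 66% against about 80% for 23 enrolled. Losing a single patient from 19 would already lower power to 73.4%.

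These figures assume a true control rate of 0.90, the plan's 20% dropout occurring independently between patients and unrelated to outcome, and a test run on however many patients are evaluable with the cut-off reset to keep 0.025. The size of the loss changes with the dropout rate; the inconsistency between the sections does not.

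**What to change.** Restate the synopsis as: minimum 19 evaluable patients (about 24 enrolled at 20% dropout, since 19/0.80 = 23.75); up to 35 consented, including screen failures. The sponsor should confirm that 35 is meant as a count of consented people.

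Use the same terms in 9.2 and 9.4.6, and change 23 to 24 there. As written, 23 enrolled gives 18.4 expected evaluable patients at the stated dropout.

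Do not define enrolled as having started brigatinib. Section 9.3 lists enrolling and starting drug as separate conditions, and 9.4.1 builds the full analysis set on enrolment and the safety set on treatment, so that definition would merge the two sets.

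The cost is a wording change in three places and one extra planned patient, within the existing ceiling of 35. The design, the test and the analysis populations are unchanged.

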1.2 STUDY SCHEMA

*Patients with prior exposure to brigatinib, alectinib, lorlatinib, and ceritinib are excluded.

1.3 SCHEDULE OF EVENTS

	Screen/ Enroll	Year 1							Year 2 (Week)				Survival Follow Up
		Day		Week									
Procedures	≤28 days Day 1	Day 1	Day 8 ^c	3 ^c	13 ^d	26 ^e	39 ^e	52 ^e	65 ^e	78 ^e	91 ^e	104 ^e	Termination ^j
Informed Consent/Review Eligibility	X												
Medical History	X												
MRI Brain	X			X	X	X	X	X	X	X	X	X	X
QOL Assessments ^b		X		X	X	X	X	X	X	X	X	X	X
Clinic Visit (complete physical exam)	X	X	X	X	X	X	X	X	X	X	X	X	X
ECOG Performance Status	X	X	X	X	X	X	X	X	X	X	X	X	X
Pregnancy Test (WOCBP only) ^g	X												
Concomitant Meds (including corticosteroids agent and dose)	X	X	X	X	X	X	X	X	X	X	X	X	X
Adverse Events ^h	X	X	X	X	X	X	X	X	X	X	X	X	X
Labs (CBC, CMP, CPK, Lipase, Amylase)	X	X	X	X	X	X	X	X	X	X	X	X	X
Research Blood for cfDNA	X												X
RECIST 1.1/RANO-BM	X			X	X	X	X	X	X	X	X	X	X
Systemic Imaging (CT C/A±P or PET/CT)	X ⁱ			X	X	X	X	X	X	X	X	X	X
Brigatinib Administration ^a		X	X	X	X	X	X	X	X	X	X	X	
CNS Radiation for Brain Metastases Progression (as indicated per PI/Sub-I)													X ⁱ
Vitals Collection (BP, spO ₂ and HR)	X	X	X	X	X	X	X	X	X	X	X	X	X
Survival and Disease Status, Current Therapy													X

3-month intervals are defined as 13 weeks (52 weeks per 12 months / 4)

^a All patients will be started on brigatinib 90 mg daily for 7 days, before escalating to 180 mg daily thereafter as tolerated

^b EORTC QLQ-C30 and BN20 brain-specific questionnaire

^c Day 8 and Week 3 procedures have a window of \pm 4 days from Day 1

^d Week 13 procedures have a window of \pm 7 days

^e All time points 26 weeks and onwards inclusive have a window of \pm 14 days

^f For patients removed from study treatment prior to 24 months (Week 104), survival follow-up will be done every 6 months (\pm 14 days from Termination Visit) for up to 24 months from Day 1, or until death or patient withdrawal of consent; this includes for patients who develop CNS progression while on study

^g Pregnancy Test (for WOCBP only) should also be performed prior to any radiation therapy subsequent to enrollment including radiation for brain or extracranial disease according to SOC.

^h Baseline neurologic symptoms should be scored per Cox, James D., et al "Toxicity criteria of the radiation therapy oncology group (RTOG) and the European organization for research and treatment of cancer (EORTC)." *International Journal of Radiation Oncology• Biology• Physics* 31.5 (1995): 1341-1346. Only patients with neurologic symptoms from their brain metastases that are grade 0, 1, 2 are eligible for inclusion; patients with grade 3 and 4 neurologic symptoms are excluded (see section 5). Scale: Grade 0 (no neurologic symptoms), Grade 1 (Fully functional status (i.e., able to work) with minor neurological findings, no medication needed), Grade 2 (Neurological findings present sufficient to require home care/nursing assistance may be required/medications including steroids/antiseizure agents may be required), Grade 3 (Neurological findings requiring hospitalization for initial management), Grade 4 (Serious neurological impairment that includes paralysis, coma, or seizures > 3 per week despite medication/hospitalization required)

ⁱCNS salvage radiation therapy will be done in the event of brain metastases progression, per treating investigator

^jFor patients discontinuing study treatment prior to Week 104, termination visit assessments (other than CNS salvage therapy, if required) are to occur within 30 days of last dose of study drug. If patient continues on study treatment until Week 104, the study termination visit is to occur at Week 104 (month 24) and patients may transition to SOC brigatinib at that time, if still receiving clinical benefit.

^k Baseline systemic imaging (CT or PET/CT only) performed per standard of care within 6 weeks (42 days) of Day 1 will be permitted

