4. To evaluate the time until the administration of WBRT with brigatinib alone	4. Time until the administration of whole brain-radiotherapy (WBRT) and rates at follow up intervals (up to 24 months from Day 1).	It is important to characterize the time until WBRT with a strategy brigatinib alone, as WBRT is associated with known toxicities.
5. To evaluate longitudinal changes in quality of life with brigatinib alone	5. Quality of life will be assessed using standardized QOL metrics (EORTC QLQ C30/BN 20)	It is important to characterize the longitudinal QOL achieved with a strategy of brigatinib alone.
Exploratory		
1. Analysis of blood at baseline and at progression to correlate with clinical outcomes.	1. Evaluation of cfDNA and/or other blood-based markers at baseline and progression to correlate with clinical outcomes including disease recurrence, survival, and quality of life	Evaluations of cfDNA can offer important insights into prognostic and predictive biomarkers for patients with metastatic ALK+ NSCLC with brain metastases.
2. To characterize corticosteroids	2. Quantification of the agent and dosage of corticosteroids at each study assessment	It is important to quantify the effect of brigatinib on corticosteroid requirements

administration before and after brigatinib initiation		because corticosteroids can be associated with symptoms and negative effects on quality of life
---	--	---

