4 STUDY DESIGN

4.1 OVERALL DESIGN

This is a single arm phase-II study including patients with ALK+ NSCLC and brain metastases, who are either neurologically asymptomatic or have only mild neurologic symptoms (RTOG acute neurologic morbidity score 0-2) from their brain metastases, who are TKI naïve or have had prior exposure to crizotinib, but who are naïve to brigatinib and other ALK TKIs including alectinib, lorlatinib, and ceritinib. At screening and enrollment, patients will have a history and physical exam, CTCAE symptoms assessment, and brief QOL questionnaires.

At day 1, all patients will be started on brigatinib 90 mg daily for 7 days, before escalating to 180 mg daily thereafter as tolerated.

At day 8, patients will be seen for a scheduled clinic visit. Each clinic visit will include toxicity assessment and physical exam. Day 8 procedures have an allowable window of ± 4 days. Brief QOL questionnaires will be administered at baseline (Day 1), at 3 weeks (Day 21), and at 3 months (week 13) and subsequent visits every 3 months.

At 3 weeks (Day 21), patients will be seen for scheduled clinic visits and a scheduled surveillance brain MRI. Week 3 procedures have an allowable window of ± 4 days. Subsequently, patients will have scheduled clinic visits and surveillance brain MRIs at 3 months post enrollment (week 13) and at 3 month intervals for year 1 and 2 (ie, at week 26, 39, 52, 65, 78, 104).

Patients who develop CNS progression during the study will be offered palliative radiation for their brain metastases and their disease status will be recorded as CNS progression event.

Patients who experience disease progression per RECIST 1.1 or RANO BM may continue to be treated with brigatinib if, in the opinion of the treating investigator, they continue to experience clinical benefit. Note, this is an accepted treatment strategy per the contemporary NCCN NSCLC guidelines. In this case, patients will be removed from study treatment and will be followed for survival for up to 24 months from Day 1, but may continue to receive brigatinib per standard of care.

If patients do not experience disease progression, they will complete the study treatment at 24 months. Patients continuing to benefit from brigatinib in the opinion of the treating physician may remain on the drug after 24 months per standard of care.

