6.5 PROHIBITED THERAPY

At enrollment, additional systemic therapies for the treatment of lung cancer may not be taken concomitantly with brigatinib (eg, TKIs, immunotherapy, chemotherapy), but there will not be a

required washout period for prior systemic therapies, with the exception of systemic treatment with strong cytochrome p-450 (cyp)3a inhibitors, strong cyp3a inducers, or moderate cyp3a inducers, which are not permitted within 14 days of study enrollment (refer to current brigatinib IB version for comprehensive list).

Patients may be switched to regimens containing these therapies by the treating physician if brigatinib is discontinued due to progressive disease or brigatinib intolerance by the patient. Disease progression and the associated changes in therapy will be recorded, the patient will be removed from study treatment, and they will continue to be followed for survival (for up to 24 months from Day 1).

Use of alternative or herbal therapy while on study treatment is only allowed if no known interactions with the study medication exist and must be documented and approved by the sponsor.

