9.4.8 EXPLORATORY ANALYSES

Blood will be collected at baseline and at progression. For exploratory analyses, circulating free (cf) DNA levels and/or other blood-based markers will be correlated with measured study endpoints including overall survival, disease progression, and quality of life.

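### The cfDNA progression sample is triggered by the end of study treatment, not by progression, and may be drawn after radiation or a new regimen

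*Combined protocol and SAP*

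**What the plan says.** Section 3 gives the first exploratory endpoint as "Evaluation of cfDNA and/or other blood-based markers at baseline and progression to correlate with clinical outcomes including disease recurrence, survival, and quality of life". Section 9.4.8 repeats the two time points, "Blood will be collected at baseline and at progression", and says that the marker levels "will be correlated with measured study endpoints including overall survival, disease progression, and quality of life".

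The schedule in section 1.3 has one row for this, "Research Blood for cfDNA", marked at Screen/Enroll and at Termination and nowhere else. Footnote j sets the Termination visit. For patients who stop before Week 104, "termination visit assessments (other than CNS salvage therapy, if required) are to occur within 30 days of last dose of study drug"; for patients still on study treatment it falls at Week 104.

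Two sections link progression to the end of study treatment. Section 4.1 covers progressors who carry on with brigatinib because they still benefit: "In this case, patients will be removed from study treatment and will be followed for survival for up to 24 months from Day 1". Section 6.5 covers those who change drug: "Patients may be switched to regimens containing these therapies by the treating physician if brigatinib is discontinued due to progressive disease", after which they too come off study treatment and are followed for survival. Section 7.2 has a narrower list of mandatory reasons to stop: it names progression only where the investigator judges that another therapy is needed.

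**The concern.** The objective and the analysis section define the second sample by a disease event, while the schedule defines it by the end of dosing. A site that follows the schedule exactly can draw the sample after salvage radiation or after a new drug has started. That sample no longer describes progression on brigatinib alone. The site will also draw the same tube from patients who stopped for toxicity or finished two years without progressing.

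Labels can be repaired afterwards from the recorded progression dates, but timing cannot. With about 23 patients planned (section 9.2) and only some of them progressing, each mistimed sample is a noticeable loss to this objective.

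**Working it through.** The plan attaches no figure to this point, so the check sets the sections side by side.

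1. **Where blood is drawn and where progression is read.** The schedule has 13 columns. cfDNA blood is marked in 2 (Screen/Enroll, Termination). RECIST/RANO-BM is marked in 11 (Screen/Enroll; Weeks 3, 13, 26, 39, 52, 65, 78, 91 and 104; Termination). Removing the two columns that carry blood leaves 11 − 2 = 9 on-treatment visits. Week 104 doubles as Termination for patients still on treatment, so 9 − 1 = 8 visits, Weeks 3 to 91, can reveal progression with no cfDNA draw marked.

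2. **Route from progression to the draw.** Under sections 4.1 and 6.5 a progressor leaves study treatment, which brings on the Termination visit and its tube. This is the normal path. Brain MRI, systemic imaging and response assessment are marked in the same column.

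3. **Length of the gap.** Time from progression to draw = (progression to last study-drug dose) + (last dose to Termination). Footnote j caps the second term at 30 days for early stoppers. Nothing caps the first. It is unclear in two cases:
   - A progressor who moves to standard-of-care brigatinib under section 4.1: the documents do not say which dose counts as the last one.
   - A progressor not judged to need another therapy: section 7.2 read alone does not require study treatment to stop, whereas section 4.1 takes the patient off it. If such a patient progressed at Week 13 and stayed on study treatment to Week 104, the gap would be 104 − 13 = 91 weeks. This is an extreme case under one reading, not a forecast; it shows that 30 days is not an upper limit on the gap from progression.

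4. **Order relative to the next treatment.** Footnote j leaves CNS salvage therapy outside the 30-day window, and footnote i leaves radiation to the treating investigator. Neither says that the blood comes first. The protocol does set such an order elsewhere: footnote g asks for a pregnancy test before any radiation.

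5. **Who gives the tube.** Footnote j applies whatever the reason for stopping, and to Week 104 completers. No text says which Termination tubes count as progression samples.

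6. **Use in the analysis.** Section 9.4.8 does not say which sample is related to which endpoint, and gives no time origin for the second one. The time-to-event endpoints are followed to 24 months from Day 1. Section 4.4 and footnote f keep survival follow-up going to that point, so survival after the sample can be observed, though for a shorter time the later the progression.

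**The case against.** The strongest reply is that the schedule works in practice. Progression leads to removal from study treatment, removal leads to Termination, and the tube is drawn at a visit that also carries imaging and response assessment. Thirty days is an outer limit counted from the last dose, not an expected lag after progression. Progression status and dates are needed anyway for secondary endpoints 1a to 1d, so tubes from non-progressors can be found and set aside. All of this stands. It answers the labelling problem, but not the order relative to radiation or a new drug, nor the case of a progressor who stays on study treatment.

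A reader might infer more than the documents support:

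- *That the progression marker cannot be derived at all.* Sections 4.1 and 6.5 route most progressors to a sample near progression.
- *That a paired baseline-versus-progression comparison is undermined.* Section 9.4.8 plans correlations with outcomes and names no paired contrast. The baseline correlations are untouched.
- *That samples from progressors and non-progressors will be pooled.* No text says so, and section 9.4.8 speaks only of progression.
- *That immortal-time bias is built in.* It would arise only if the second sample were related to times counted from Day 1. The plan is silent on the origin, which is a gap and not a stated error.
- *That the second sample cannot be set against quality of life.* The questionnaires are also marked at Termination, so a concurrent correlation is possible.

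**Conclusion.** The schedule and the exploratory objective disagree about what triggers the second cfDNA sample, and the disagreement has a practical consequence: following the schedule exactly permits a draw after CNS radiation or a regimen change, or long after progression. Sections 4.1 and 7.2 must also be reconciled on whether a progressor can remain on study treatment, because the timing of the draw depends on it.

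The number of affected patients cannot be computed. The documents give no expected progression rate and no split of discontinuations by reason; a count would only restate an assumed progression rate and would still not show how many progressors were sampled after further treatment. The conclusion rests on the text of the schedule and its footnotes and needs no such assumption. Only an exploratory endpoint is affected. The primary endpoint, the sample size and the power are unchanged. It is worth correcting because a sample missed at the right moment cannot be replaced.

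**What to change.** Add a footnote to the "Research Blood for cfDNA" row. In patients who progress, the second sample is drawn at, or as soon as possible after, first documented RANO-BM or RECIST progression, and before subsequent anticancer therapy where feasible without delaying care. It takes the place of their Termination draw. Patients without progression keep the Termination or Week 104 draw, labelled as end of treatment, no progression.

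Add two sentences to section 9.4.8. First, only progression-triggered samples count as progression samples. Second, their association with survival is measured from the sample date, while baseline markers are related to the endpoints counted from Day 1. Reconcile sections 4.1 and 7.2 on study treatment after progression, and state which dose is the last study-drug dose when brigatinib continues as standard of care.

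The number of planned samples per patient stays at two. The cost is one footnote, two sentences and the reconciliation. Some draws will be missed, or will need a separate venipuncture, when the scan is read after the visit or when an equivocal new lesion is confirmed later and progression is dated back to the initial scan (section 8.1.1). In that last case the actual sample date should be recorded and used.
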